6.3.1 Definition of BED

Biologically effective dose (BED) is defined as the dose of oral decitabine (ASTX727) that results in at least a 10% decrease in LINE-1 methylation level from the baseline sample to the 8 week post baseline tumor sample in at least 50% of patients treated within a dose level. As LINE-1 (long interspersed element-1) is a repetitive DNA retrotransposon that duplicates via a copy-and-paste genetic mechanism. As LINE-1 constitutes approximately 17% of the human genome, the extent of LINE-1 methylation is regarded as a surrogate marker of global DNA methylation. ASTX Pharmaceuticals has assessed changes in LINE-1 methylation with ASTX727 as a marker of efficacy in their prior clinical trials. The change in LINE-1 methylation is a working rule and a panel of markers will be assessed and the dose with the most viable panel and lowest adverse event profile will be used in the expansion cohort of the study.

6.4 Definition of DLT

Dose-limiting toxicities (DLTs) will be evaluated during the dose escalation phase of the trial. The period for evaluating DLTs will be from the time of first administration of oral decitabine (ASTX727) until after 28 days after the first dose of oral decitabine (ASTX727), durvalumab (MEDI4736), and tremelimumab combination therapy (end of Cycle 2 (which is the first cycle of the triple combination)).

Subjects who do not remain on the study up to this time for reasons other than DLT will be replaced with another subject at the same dose level. Grading of DLTs will follow the guidelines provided in the Common Terminology Criteria for Adverse Events (CTCAE) version 4.03.

A DLT will be defined as any Grade 3 or higher toxicity that occurs during the DLT evaluation period. Toxicity that is clearly and directly related to the primary disease or to another etiology is excluded from this definition. The following will be DLTs:

- Any Grade 4 irAE
- Any \geq Grade 3 colitis
- Any Grade 3 or 4 noninfectious pneumonitis irrespective of duration
- Any Grade 2 pneumonitis that does not resolve to ≤ Grade 1 within 3 days of the initiation of maximal supportive care
- Any Grade 3 irAE, excluding colitis or pneumonitis, that does not downgrade to Grade 2 within 3 days after onset of the event despite optimal medical management including systemic corticosteroids or does not downgrade to ≤ Grade 1 or baseline within 14 days
- Liver transaminase elevation $> 8 \times ULN$ or total bilirubin $> 5 \times ULN$
- Any ≥ Grade 3 non-irAE, except for the exclusions listed below
- Grade 4 neutropenia lasting > 10 days or accompanied by fever (defined as > 38.5°C requiring

hospitalization)

• Grade 3 thrombocytopenia with clinically significant bleeding

The definition excludes the following conditions:

- Grade 3 fatigue lasting \leq 7 days
- Grade 3 endocrine disorder (thyroid, pituitary, and/or adrenal insufficiency) that is managed
 with or without systemic corticosteroid therapy and/or hormone replacement therapy and the
 subject is asymptomatic
- Grade 3 inflammatory reaction attributed to a local antitumor response (eg, inflammatory reaction at sites of metastatic disease, lymph nodes, etc)
- Concurrent vitiligo or alopecia of any AE grade
- Grade 3 infusion-related reaction (first occurrence and in the absence of steroid prophylaxis) that resolves within 6 hours with appropriate clinical management
- Grade 3 or 4 neutropenia that is not associated with fever or systemic infection that improves by at least 1 grade within 3 days. Grade 3 or Grade 4 febrile neutropenia will be a DLT regardless of duration or reversibility
- Grade 3 or 4 lymphopenia
- Grade 3 thrombocytopenia that is not associated with clinically significant bleeding that requires medical intervention, and improves by at least 1 grade within 3 days
- Isolated Grade 3 electrolyte abnormalities that are not associated with clinical signs or symptoms and are reversed with appropriate maximal medical intervention within 3 days
- Grade 3 emesis that responds to optimal antiemetic therapy within 72 hours
- Grade 3 diarrhea that responds to optimal medical management within 72 hours

Immune-related AEs are defined as AEs of an immune nature (ie, inflammatory) in the absence of a clear alternative etiology. In the absence of a clinically significant abnormality, repeat laboratory testing will be conducted to confirm significant laboratory findings prior to designation as a DLT.

If a DLT occurs, the patient will be removed from further treatment in the protocol. The patient will be followed for their DLT until there is complete resolution of the observed toxicity. These toxicities will effect dose escalation decisions. Any occurrence of grade 4 or greater toxicity will prompt the sponsor and the principal investigator to conduct a thorough evaluation of the available safety information to justify a decision to enroll new subjects into the study.

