6.3 Dose Escalation Decision Rules

Dose escalation monitoring

In order to ensure that patients are receiving the assigned dose of drug, oral decitabine (ASTX727), several measures will be employed.

Printed orders will be available.

The principal investigator, research nurse, and data manager will review the available toxicity data prior to continuing to escalate the dose and enrolling patients into the new cohort.

Prior to the start of each new dose level (i.e. accrual of a new cohort), a dated letter will be sent to the pharmacy which describes the change in dose.

Stopping rules

Dose escalations will continue until one of the following stopping rules has been satisfied:

- 1. The BED has been determined.
- 2.If at any time during accrual to a cohort, 2 or more patients in a dose cohort experience DLT, enrollment to that dose cohort will be terminated and dose escalation will stop.
- 3. Two of six patients treated at a reduced dose of oral decitabine (ASTX727) on Days 1-2 of a 28 day cycle experience a DLT

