in bowel habits, medical intervention indicated, peritoneal signs; Grade 4 Colitis: lifethreatening consequences, urgent intervention indicated)

(Grade 3 Perforation: severe symptoms, elective* operative

intervention indicated; Grade 4 Perforation: life-threatening consequences, urgent intervention indicated)

Grade 3

Permanently discontinue study drug/study regimen for Grade 3 if toxicity does not improve to Grade ≤1 within 14 days; study drug/study regimen can be resumed after completion of steroid taper.

Grade 4

Permanently discontinue study drug/study regimen.

For Grade 3 or 4:

- Promptly initiate empiric IV methylprednisolone 2 to 4 mg/kg/day or equivalent.
- Monitor stool frequency and volume and maintain hydration.
 - Urgent GI consult and imaging and/or colonoscopy as appropriate.
 - If still no improvement within 3 to 5 days of IV methylprednisolone 2 to 4 mg/kg/day or equivalent, promptly start further immunosuppressives (e.g., infliximab at 5 mg/kg once every 2 weeks). Caution: Ensure GI consult to rule out bowel perforation and refer to infliximab label for general guidance before using infliximab. If perforation is suspected, consult a surgeon experienced in abdominal surgery immediately without any delay.
- Once the patient is improving, gradually taper steroids over
 ≥28 days and consider prophylactic antibiotics, antifungals, and
 anti-PJP treatment (refer to current NCCN guidelines for
 treatment of cancer-related infections).^a

*This guidance anticipates that Grade 3 operative interventions of perforations are usually not elective

Hepatitis (elevated LFTs)

Date 09202024

Infliximab should not be used for management of immune-related hepatitis.

PLEASE SEE
shaded area
immediately below
this section to find
guidance for
management of
"Hepatitis (elevated
LFTS)" in HCC
patients

Any Elevations in AST, ALT or TB as Described Below

AST or ALT >ULN
and ≤3.0×ULN if
baseline normal, 1.53.0×baseline if
baseline abnormal;
and/or TB > ULN and
≤1.5×ULN if baseline
normal, >1.01.5×baseline if

baseline abnormal

as v

No dose modifications. If it worsens, then treat as described for elevations in the row below.

General Guidance

AST or ALT >3.0×ULN and ≤5.0×ULN if baseline normal, >3-5×baseline if baseline abnormal; and/or TB >1.5×ULN and ≤3.0×ULN if baseline

- Hold study drug/study regimen dose until resolution to AST or ALT ≤3.0×ULN and/or TB ≤1.5×ULN if baseline normal, or to AST or ALT ≤3.0×baseline and/or TB

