- Resume study drug/study regimen if elevations downgrade to AST or ALT ≤3.0×ULN and/or TB ≤1.5×ULN if baseline normal, or to AST or ALT ≤3.0×baseline and/or TB ≤1.5×baseline if baseline abnormal, within 14 days and after completion of steroid taper.
 - Permanently discontinue study drug/study regimen if the elevations do not downgrade as described in bullet above within 14 days

For elevations in transaminases >8×ULN or elevations in TB >5×ULN if baseline normal, or for elevations in transaminases

- Promptly initiate empiric IV methylprednisolone at 1 to 4 mg/kg/day or equivalent.
- If still no improvement within 3 to 5 days despite 1 to 4 mg/kg/day methylprednisolone IV or equivalent, promptly start treatment with immunosuppressive therapy (i.e., mycophenolate mofetil). Discuss with study physician if mycophenolate is not available. Infliximab should NOT be used.
- Request Hepatology consult, and perform abdominal workup and imaging as appropriate.
- Once the patient is improving, gradually taper steroids over ≥28 days and consider prophylactic antibiotics, antifungals, and anti-PJP treatment (refer to current NCCN guidelines for treatment of cancer-related infections).^a

CONFIDENTIAL AND PROPRIETARY
TMGs, Version 17 October 2019, CTCAE v4.03

>8×baseline and/or TB >5×baseline if baseline abnormal, permanently discontinue study drug/study regimen.

Permanently discontinue study drug/study regimen for any case meeting Hy's law criteria (AST and/or ALT >3 × ULN + bilirubin >2 × ULN without initial findings of cholestasis (i.e., elevated alkaline P04) and in the absence of any alternative cause.^b

Hepatitis	Any Elevations in	General Guidance	For Any Elevations Described:
(elevated LFTs)	AST, ALT or TB as		 Monitor and evaluate liver function test: AST, ALT, ALP, and TB.
Infliximab should not be used for management of immune-related hepatitis.	Described Below		Evaluate for alternative etiologies (e.g., viral hepatitis, disease progression, concomitant medications, worsening of liver cirrhosis [e.g., portal vein thrombosis]).
THIS shaded area			For HBV+ patients: evaluate quantitative HBV viral load, quantitative HBsAg, or HBeAg
is guidance only for			 For HCV+ patients: evaluate quantitative HCV viral load
management of			 Consider consulting hepatologist/Infectious Disease specialist regarding change/implementation in/of antiviral medications
"Hepatitis (elevated			for any patient with an elevated HBV viral load >2000 IU/ml

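### The DLT definition in Section 6.4 has no item for a combined AST/ALT and bilirubin rise, so a Hy's law case below Grade 3 on both tests stops the drug but does not automatically count toward the two-DLT rule

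*Combined protocol and SAP*

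**What the plan says.** Section 6.4 opens with a general rule: "A DLT will be defined as any Grade 3 or higher toxicity that occurs during the DLT evaluation period". Of the items listed after it, the only one specific to the liver is "Liver transaminase elevation $> 8 \times ULN$ or total bilirubin $> 5 \times ULN". Other liver events can enter as a Grade 4 immune-related event, as a Grade 3 or higher event that is not immune-related, or as a Grade 3 immune-related event that does not downgrade in time. One listed item names a grade below 3: "Any Grade 2 pneumonitis that does not resolve to ≤ Grade 1 within 3 days of the initiation of maximal supportive care".

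The main hepatitis table in Appendix 1 contains three permanent stops:

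- single-test limits: "For elevations in transaminases >8×ULN or elevations in TB >5×ULN if baseline normal", with matching multiples of baseline if baseline is abnormal;
- failure to recover: "Permanently discontinue study drug/study regimen if the elevations do not downgrade as described in bullet above within 14 days";
- the combined criterion: "Permanently discontinue study drug/study regimen for any case meeting Hy's law criteria (AST and/or ALT >3 × ULN + bilirubin >2 × ULN", in the absence of early cholestasis and of any alternative cause.

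Section 6.3 stops escalation on the DLT count: if "2 or more patients in a dose cohort experience DLT, enrollment to that dose cohort will be terminated and dose escalation will stop". Section 11 sets the cohort size at six.

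**The concern.** A moderate transaminase rise and a moderate bilirubin rise occurring together, with no other explanation, suggest drug-induced liver injury more strongly than either value alone. Appendix 1 recognises this by requiring a permanent stop at levels where each test taken singly would lead only to a hold. Section 6.4 has no corresponding item, so the event that ends treatment for that patient may be recorded as no DLT.

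What is at stake is the escalation decision. With one ordinary DLT and one such case in a cohort, the formal count is one of six, which permits the next dose level. With the case included it would be two of six, which stops the cohort. In the ASTX727 cohorts this matters mainly in Cycle 2, because Appendix 1 covers durvalumab and tremelimumab, and durvalumab starts in that cycle.

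**Working it through.** **Step 1. Locate the gap.** Inputs: the Section 6.4 limits (8 and 5 times ULN, each test alone); the Hy's law thresholds in Appendix 1 (above 3 and above 2 times ULN); and Grade 3 taken to begin above 5 times ULN for AST/ALT and above 3 times ULN for bilirubin. The last input is an assumption, because the protocol names CTCAE 4.03 without printing the cut-offs. The upper ends of the Appendix 1 hold row fit it: "AST or ALT >3.0×ULN and ≤5.0×ULN if baseline normal, >3-5×baseline if baseline abnormal; and/or TB >1.5×ULN and ≤3.0×ULN if baseline".

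| AST/ALT (×ULN) | Bilirubin (×ULN) | Hy's law thresholds met | Section 6.4 liver item met | Grade 3 on either test |
|---|---|---|---|---|
| 3.5 | 2.2 | yes | no | no |
| 4 | 2.5 | yes | no | no |
| 5 | 3 | yes | no | no |
| 6 | 2.5 | yes | no | yes |
| 9 | 2.5 | yes | yes | yes |

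The first three rows lie in the gap: AST/ALT above 3 and up to 5, bilirubin above 2 and up to 3. Higher values reach Grade 3 on at least one test. Immune-related cases at 5–8 or 3–5 times ULN that downgrade in time are ambiguous, because the opening sentence of Section 6.4 would count them and its immune-related item would not. The point does not rely on them.

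**Step 2. Effect given one such case.** The plan states no operating characteristics for its DLT rule, so there is no figure to reproduce. In a cohort of six with one uncounted case, the decision changes if exactly one of the other five has a DLT. With DLT rate p this is 5p(1−p)⁴:

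| p | 5% | 10% | 15% | 20% | 30% |
|---|---|---|---|---|---|
| probability | 20.4% | 32.8% | 39.2% | 41.0% | 36.0% |

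**Step 3. Effect over all cohorts.** Let q be the rate of uncounted cases per patient, and let T(x) = 1 − (1−x)⁶ − 6x(1−x)⁵ be the chance of two or more events in six. The share of cohorts whose decision changes is T(p+q) − T(p). For example, at p = 20% and q = 1%, T(0.21) − T(0.20) = 36.9% − 34.5%, about 2.5% before rounding.

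| q (assumed) | Share of cohorts changed, p = 5–30% |
|---|---|
| 0.05% | 0.06–0.12% |
| 0.1% | 0.12–0.25% |
| 0.5% | 0.6–1.2% |
| 1% | 1.3–2.5% |

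The documents give no rate for q. Section 1.4.2.1 reports treatment-related Grade 3 or higher AST increases in 7 of 694 patients on durvalumab alone (1.0%). That is a different event: the gap excludes Grade 3 AST by definition, needs a bilirubin rise as well, and falls mainly within one 28-day cycle. The 1% row is therefore better read as a high illustration than as an estimate.

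**The case against.** The strongest reply is that this protocol does not treat every permanent stop as a DLT. A Grade 3 infusion reaction ends treatment under Sections 4.3 and 5.1.5, yet Section 6.4 excludes a first one that resolves within 6 hours. Appendix 1 also has other stops below Grade 3 without a matching DLT item, such as Grade 2 myocarditis that does not improve rapidly. This stands. A reader might infer that Section 6.4 was meant to reproduce the Appendix 1 hepatic stops and dropped one by mistake; the documents do not support that. The argument for inclusion has to rest on the seriousness of probable drug-induced liver injury, the same kind of reasoning that admits unresolved Grade 2 pneumonitis.

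Second, a count below two does not compel escalation. Section 6.1.2 opens the second cohort only if that is safe, Sections 6.2 and 11 put the same condition on the third dose level, and Section 6.3 requires a review of toxicity data first. Choice of the expansion dose also considers the adverse event profile (Sections 6.3.1 and 11). This stands too: the investigator may hold. These are matters of judgement, however, and none makes the case count or requires a hold.

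Third, the patient is protected. Drug stops permanently, Section 10.3.3.2 requires reporting of hepatic abnormality within 24 hours, and the DSMC reviews toxicity about quarterly. The remaining issue concerns the dose decision for later patients.

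Finally, an investigator might grade the diagnosis itself as Grade 3, in which case it may count. That is possible, but it leaves the outcome to individual grading.

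**Conclusion.** The gap holds in a narrow form. A Hy's law case with AST/ALT above 3 and up to 5 times ULN and bilirubin above 2 and up to 3 times ULN must permanently stop drug under Appendix 1, but does not automatically count toward the two-DLT rule. This rests on the assumed CTCAE cut-offs.

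The expected effect is small. The 20–41% applies only once such a case has occurred. Over all cohorts the change is about 0.06–0.25% at case rates of 0.05–0.1%, and 1.3–2.5% at 1%; all these rates are assumptions.

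Two stronger readings should not be drawn. The plan does not force escalation after such a case. Nor does it clearly remove the patient from the cohort: the replacement sentence in Section 6.4 concerns patients who do not remain on the study, whereas Section 4.3 treats stopping drug separately and keeps such patients in follow-up. This is a worthwhile clarification for safety and of low priority.

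**What to change.** At the next amendment, add a third alternative to the hepatic item in Section 6.4: AST and/or ALT above 3 times ULN together with bilirubin above 2 times ULN, with no cholestasis at presentation and no other cause found, citing the Hy's law criterion in Appendix 1. Leave the existing 8 and 5 times ULN limits as they are. The condition on other causes must stay in, because Section 4.1 admits patients with liver metastases whose AST/ALT is up to 5 times ULN.

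The cost is one clause. No tests are added: AST, ALT, alkaline phosphatase and bilirubin are already in Table 11, and Appendix 1 already asks for alternative causes to be examined. There are two downsides. DLT status has to wait for that examination, and a dose level may stop slightly more often. At an assumed 1% case rate, the chance of stopping a six-patient cohort rises from 3.3% to 4.6% at a 5% DLT rate, and from 34.5% to 36.9% at a 20% DLT rate.

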Results from clinical trials and other studies demonstrate that the most common toxicities associated with azacitidine are gastrointestinal (nausea, vomiting, diarrhea, constipation, anorexia), constitutional (fatigue, fever, rigors), musculoskeletal and connective tissue (arthralgia, pain in limb, weakness), pulmonary (cough, dyspnea), skin or soft tissue (injection site bruising from SC injection, rash, erythema), and hematologic (neutropenia, anemia, leukopenia). Nausea, vomiting and diarrhea are among the most common adverse effects of azacitidine and appear to be self-limiting with repeated cycles of therapy. Myelosuppression also occurs in a majority of patients, and accounts for the most common reason of dose reduction and treatment termination during clinical trials. Infrequent adverse effects include neuromuscular aches, generalized weakness, renal tubular acidosis, and liver enzyme abnormalities. Erythema and burning at the injection site can occur following SC administration, which usually resolves within 24-72 hours.

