Although assessment of the BED is primary, the dose also needs to be safe. Each dose will also be assessed for safety. Six patients will be entered into dose level 1. Adverse events (i.e. dose limiting toxicity (DLT) assessment as defined in section 6.4) will be assessed through 28 days post cycle 2. If two or more of the first six subjects experience a DLT, then the dose will be reduced and an additional six patients will be treated at the reduced dose. If two or more of the six at the reduced dose experience a DLT, then the study will be terminated. If at any time during accrual to a dose cohort, 2 or more patients in a dose cohort experience DLT, enrollment to that dose cohort will be terminated. If less than two of the six patients treated at dose level 1 experience a DLT, a subsequent group of six patients will receive dose level 2.

Drug Substance Azacitidine/Decitabine (ASTX727)

Study Code 15-11430

Edition Number 13.0

Date 09202024

Accrual will be suspended until review of the BED rate in tissue from baseline and 8 weeks post baseline has been completed from patients entered into the first 2 dose levels. If the BED has not been determined in the first 2 dose levels and it is safe to do so, then the study will re-open to accrual and a subsequent group of 6 patients will receive the 3rd dose level. Once the BED is determined, dose escalation will stop and the BED will be used in the expansion cohort.

Approximately 28 evaluable patients (eligible patients who at least begin protocol treatment and have an evaluable pre- and on-treatment (8-week) biopsy sample available) are estimated to be accrued during the BED assessment phase with the oral decitabine. This is based on studying 6 evaluable patients per dose level with a total of 3 dose levelsand an additional 10 evaluable patients entered at the BED ('expansion cohort' accrued to ensure that the BED rate is acceptable). The further assessment of the BED will be based on studying these 10 additional patients. Additional subjects may be enrolled into the cohort(s) to ensure that the required number of evaluable pre- and on-treatment biopsy samples are available to adequately determine the BED. See end of this statistical section for overall sample size.

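### Section 6.4 sets two incompatible duration tests for afebrile, uninfected Grade 4 neutropenia: an episode of more than 3 and up to 10 days is a DLT on one reading and not on the other

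*Combined protocol and SAP*

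**What the plan says.** Section 6.4 starts from a broad rule, "A DLT will be defined as any Grade 3 or higher toxicity that occurs during the DLT evaluation period", and sets aside toxicity clearly due to the disease or another cause. A list of DLT items follows, and then a list of excluded conditions. Three lines decide how neutropenia is scored:

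- The item written for it: "Grade 4 neutropenia lasting > 10 days or accompanied by fever".
- The catch-all item: "Any ≥ Grade 3 non-irAE, except for the exclusions listed below".
- The exclusion: "Grade 3 or 4 neutropenia that is not associated with fever or systemic infection that improves by at least 1 grade within 3 days". The same bullet adds "Grade 3 or Grade 4 febrile neutropenia will be a DLT regardless of duration or reversibility".

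Neither Section 6.4 nor the rules that use it (Sections 6.2, 6.3 and 11) say which line prevails when they differ.

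The score is then used in two ways.

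- **Cohort level.** Section 6.3 says "If at any time during accrual to a cohort, 2 or more patients in a dose cohort experience DLT", that cohort closes to enrollment and escalation stops. Section 11 applies this to cohorts of six: "If less than two of the six patients treated at dose level 1 experience a DLT", six more patients go to dose level 2. With two or more DLTs the dose is reduced, and two or more of six at the reduced dose end the study.
- **Patient level.** Section 6.4 takes a patient with a DLT off protocol treatment, and Section 4.3 lists a DLT among the reasons for permanent discontinuation.

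**The concern.** A DLT definition has to give one answer for each patient, because the escalation rule only counts those answers. Here the specific item points to a limit of 10 days, while the catch-all less its exclusion points to 3 days. Two assessors who both follow Section 6.4 could score the same afebrile Grade 4 episode of, say, 6 days differently. With a threshold of two in six, one or two such patients can decide whether a cohort closes, whether the dose is reduced or whether the study ends. The score also decides whether the individual patient leaves treatment.

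**Working it through.** **Step 1: the two tests side by side.** The inputs are the three lines of Section 6.4 quoted above. The case considered is neutropenia without fever or systemic infection, classed as a non-irAE and not clearly due to disease or another cause. (A Grade 4 irAE is a DLT under its own item, so the question does not arise there.)

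| Time at Grade 4 | Item with the 10-day limit | Catch-all less the 3-day exclusion |
|---|---|---|
| Up to 3 days, then improved by a grade | not met | excluded, not a DLT |
| More than 3 and up to 10 days | not met | not excluded, DLT |
| More than 10 days | DLT | DLT |

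The tests differ only in the middle row.

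**Step 2: can both lines have effect?** Suppose any one item is enough. The middle row is then a DLT through the catch-all. Every afebrile episode beyond 10 days has already failed the 3-day exclusion, so the 10-day limit never changes a classification. Suppose instead that the specific item governs Grade 4 neutropenia. The 10-day limit then has effect, but only because the middle row is not a DLT. No reading lets the 10-day limit matter and also scores the middle row as a DLT.

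**Step 3: illustration of the effect on the stopping rule.** The plan states no probability for the DLT rule (the table in Section 11 concerns the BED), so there is no figure to reproduce. Let b be the rate of all other DLTs and q the rate of middle-row episodes, taken as independent. Both rates are assumptions. If the episodes count, the DLT rate is

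p = 1 − (1 − b)(1 − q),

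and if they do not, p = b. For a cohort of six,

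P(2 or more) = 1 − (1 − p)^6 − 6p(1 − p)^5.

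With b = 0.10:

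- Episodes not counted: p = 0.10; 1 − 0.531 − 0.354 = 0.11 (0.114 before rounding).
- Counted, q = 0.05: p = 1 − 0.90 × 0.95 = 0.145; P = 0.21.
- Counted, q = 0.10: p = 1 − 0.90 × 0.90 = 0.19; P = 0.32.
- Counted, q = 0.20: p = 1 − 0.90 × 0.80 = 0.28; P = 0.54.

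Other assumed base rates move the same way. At b = 0.05 the chance goes from 0.03 to between 0.11 (q = 0.05) and 0.44 (q = 0.20). At b = 0.20 it goes from 0.34 to between 0.44 and 0.70.

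**The case against.** The best answer is that the literal text is determinate. Section 6.4 introduces its items as things that will be DLTs, so meeting any one is enough, and nowhere does it say that Grade 4 neutropenia counts only after 10 days. On that view the middle-row episode is a DLT and the 10-day limit is merely redundant. Other items are redundant too: colitis and pneumonitis of Grade 3 or higher already fall under the opening rule. Nor is the neutropenia item wholly empty, since it carries a definition of fever. This is a fair reading and may be the one intended. It does not settle the matter, because a redundant colitis item agrees with the general rule, whereas the 10-day limit sets a different number for the same event. An assessor who assumes the number was put there for a purpose reaches the opposite score, and no stated precedence corrects that.

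There are also backstops. Section 6.4 calls for a sponsor and investigator review after any toxicity of Grade 4 or above, Section 6.3 for a toxicity review before escalation, and Section 13 for roughly quarterly review by the monitoring committee. Such an episode would therefore be looked at, but none of these provisions says how to score it.

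Two stronger readings are tempting and are not supported.

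- **Thrombocytopenia has the same conflict.** It does not. The DLT item is Grade 3 with clinically significant bleeding; the exclusion needs both the absence of such bleeding and improvement within 3 days. A non-bleeding case that does not improve in 3 days falls to the catch-all. Only one duration appears, and the lines fit together.
- **The disputed episode is the most likely toxicity.** Section 1.4.2.5 does say "Myelosuppression also occurs in a majority of patients", but of azacitidine, and the drug now being escalated is oral decitabine. Section 1.1.7 reports Grade III/IV neutropenia in 68.0% of cervical cancer cases on 2'-deoxy-5-azacitidine with cisplatin, without a split by grade, duration or fever. It also reports 3% Grade 4 neutropenia with azacitidine plus carboplatin. Neither is a rate for this event on this regimen. Taking q = 0.03 with b = 0.10 gives p = 1 − 0.90 × 0.97 = 0.127 and P = 0.17, so the effect could be well below the upper end of the illustration.

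**Conclusion.** The point holds as a conflict between two stated rules, confined to afebrile, uninfected Grade 4 neutropenia lasting more than 3 and up to 10 days. The literal union reading scores it as a DLT; the reading that gives the 10-day limit any effect does not. That the two cannot both stand follows from the text alone and needs no assumed rate.

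The size is uncertain. The documents give neither a DLT rate nor a rate of such episodes for this regimen, so the rise from 0.11 to 0.21, 0.32 or 0.54 shows how sensitive a two-in-six rule is to the choice of reading. It is not a forecast. It rests on the assumed 10% for other DLTs, on q of 5%, 10% or 20%, and on independence. The issue is worth resolving because the count drives cohort closure, dose reduction, study termination and removal of the patient from treatment.

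**What to change.** Reconcile the neutropenia item in the DLT list of Section 6.4 with the neutropenia exclusion, so that a single duration rule applies to afebrile, uninfected Grade 4 neutropenia. The sponsor must state which duration is intended; this review takes no view on that. A sentence saying how specific items, the catch-all and the exclusions rank would prevent the same question elsewhere in the list. The thrombocytopenia lines need no change on this account. The cost is protocol wording only; sample size and the stopping rule stay as they are.
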